Eplerenone is a relatively safe medication, but it can lead to raised serum potassium levels (i.e., hyperkalemia), which can be potentially life-threatening. In a large clinical trial of patients with CHF, the incidence of serious hyperkalemia, defined as a serum potassium concentration ≥ 6 mEq/L, was 5.5% in the eplerenone group and 3.9% in the placebo group. Patients with a lower creatinine clearance at baseline had a higher incidence of serious hyperkalemia.[37]

Eplerenone comes in two doses, 25 mg and 50 mg. The standard dose for treatment of hypertension is 50 mg daily. For patients with an inadequate blood pressure response to 50 mg, the dosage is increased to 50 mg twice daily. For treatment of CHF, patients are started on 25 mg, and escalated to 50 mg within four weeks. Dose adjustment in CHF patients takes place based on serum potassium levels as follows: < 5.0 mEq/L – Increase to 50 mg once daily; 5.0 – 5.4 mEq/L – Maintain dose; 5.5 – 5.9 mEq/L – Decrease to 25 mg every other day; ≥ 6.0 mEq/L – Withhold and restart at 25 mg every other day when potassium levels fall to < 5.5 mEq/L.[38]

The other notable side effects with aldosterone-receptor antagonist medications are related to cross-reactivity with sex hormone receptors. Eplerenone has a much lower incidence of anti-sex hormone effects than spironolactone. With eplerenone, sex hormone-related events, such as breast enlargement in men, breast pain, or menstrual abnormalities, have been reported in up to 2.5% of patients, although some studies reported no such events.[39-41]

Because of the elevations in serum potassium concentrations and consequent increased risk for hyperkalemia with eplerenone, use of this drug is contraindicated in patients at increased risk for hyperkalemia, including those with a serum potassium concentration > 5.5 mEq/L, type 2 diabetes and microalbuminuria, a serum creatinine concentration > 2 mg/dL in men and > 1.8 mg/dL in women, or a creatinine clearance < 50 mL/min, and during concomitant administration of potassium supplements, potassium-sparing diuretics, and/or potent CYP3A4 inhibitors.[38] It is recommended to check serum potassium and creatinine before initiating eplerenone therapy, followed by serum potassium within the first week and at one month after the start of treatment.[38]

Part II

Experimental Protocol:

Study Design

[figure not shown]
- Prospective, consecutive, non-randomized, non-blinded, non-comparative interventional pilot study
- Eligible patients will be those who present with CSCR, both acute and chronic types
- 20 patients will be enrolled; participation is voluntary and all interested patients must provide written informed consent to take part in the study

- Chronic CSCR will be defined as persistent subretinal fluid on OCT ≥ 3 months after initial presentation to the eye clinic, and $< 50\%$ reduction in fluid thickness on OCT after 3 months.
- Only one eye of a participant will be included in the study, although both eyes will be evaluated. In patients with bilateral CSCR, the worse eye will be the study eye.
- Patients will be evaluated and treated at the New England Eye Center (NEEC)
- All participants will receive a standard ophthalmic examination as well as color fundus photographs, fluorescein angiography, and macular OCT (see below for specific imaging protocol).
- Treatment will be the standard dose of eplerenone, 50 mg pills taken one pill daily over four weeks
- Subjects participation will include 4 visits to the NEEC:
 - o Treatment initiation
 - o 1 week after initiation
 - o 2 weeks after initiation
 - o 4 weeks after initiation
- Prior to initiating treatment, all subjects will have laboratory testing to confirm healthy ranges of the following lab tests will include: serum potassium, creatinine, electrolytes, liver function tests, uric acid, and fasting cholesterol.
- Serum potassium and creatinine levels will be re-tested at the 1 week visit.
- All lab tests will be repeated at the 4 week visit
- Blood pressure will be measured at each visit
- A database of enrolled participants will be maintained on a password protected desktop computer at the New England Eye Center.
- When the study is complete, all data will be de-identified and coded.

Study Assessments/Schematic

Study Protocol

-4 to 5 weeks total
 -20 patients with CSCR (Acute or Chronic)

Initial Diagnosis and Enrollment

1. In order to diagnose CSCR, patients typically undergo a routine ophthalmic examination, fundus photographs, fluorescein angiography, and OCT images. Patients may undergo fundus autofluorescence testing or indocyanine green angiography at the discretion of the physician to confirm the diagnosis of CSCR. These tests are done routinely in the eye clinic and are not included as part of the study protocol.
2. Once a potential participant with CSCR is identified, he or she will be invited to participate in this study. Participation is voluntary; potential participants may refuse to participate in this study and their medical care will not be affected in any way. Written informed consent will be obtained by one of the investigators, at the initial diagnosis visit. If the patients wish, they can consider whether or not to enroll in the study, and enroll at a later date if they so choose. If any non-English subjects are eligible for enrollment in the study, they will be enrolled using interpreters and IRB approved short forms as per the Tufts MC / TUHS IRB Short Form Policy. The investigator will discuss and explain the study to the potential participant. Special care will be taken to avoid the possibility of coercion in soliciting volunteers. Informed consent documents will be kept on file at the New England Eye Center. Strict confidentiality will be observed for participant record information required for documenting study results. The participants will be informed that the study adheres to the Health Insurance Portability and Accountability Act (HIPAA) and participants will have the opportunity to ask questions about the study. Understanding of the study will be assessed by the investigator or sub-investigator; the patient will be required to demonstrate a

clear appreciation and understanding of the facts, implications, and future consequences of being enrolled in the study.

3. Before enrollment, patients will be offered focal laser therapy and/or photodynamic therapy (PDT) if the physician feels this treatment may be warranted. Notably, there is no standard of care for either acute or chronic CSCR. It is unknown whether PDT may be more effective in treating CSCR if given sooner. In addition, prior authorization from medical insurance is needed for photodynamic therapy, and patients often have to wait a few weeks before PDT can be administered, therefore the process of prior authorization may be initiated concurrently to enrollment in this study if the physician feels PDT may be warranted after completion of the study.
4. *Screening Period:* Prior to starting eplerenone therapy, there will be a screening period (≤ 1 week) when serum potassium and creatinine will be evaluated. Patients will be excluded if they have a serum potassium concentration ≥ 5.0 mEq/L, a serum creatinine concentration > 2 mg/dL in men and > 1.8 mg/dL in women, or a creatinine clearance < 50 mL/min, or during concomitant administration of potassium supplements, potassium-sparing diuretics, and/or potent CYP3A4 inhibitors (see below under *Exclusion Criteria*). Additional serum tests of electrolytes, liver function tests, uric acid, and a fasting cholesterol panel will be obtained before initiating therapy. Although there are no exclusion criteria based on these additional laboratory tests, values will be compared to those after 1 month of therapy and abnormalities will be included in safety outcome evaluation at the end of the study. 7.5 to 10 ml of blood will be collected at this visit, as well as a urine sample.
5. Eplerenone is contraindicated in patients who have both type 2 diabetes and microalbuminuria. If a patient has type 2 diabetes, a urinalysis will be performed prior to starting treatment. Patients with type 2 diabetes and microalbuminuria will be excluded from the study.

Eplerenone is considered a pregnancy class B medication, which means that animal reproduction studies have failed to demonstrate a risk to the fetus and there are no adequate and well-controlled studies in pregnant women, or that animal studies have shown an adverse effect, but that adequate and well-controlled studies in pregnant women have failed to demonstrate a risk to the fetus in any trimester. Women of child-bearing potential will be tested for pregnancy at during the initial screening testing, with a urine pregnancy test.

Study Visits

1. After the screening period, patients will come to the NEEC for the first official study visit, the "Treatment Initiation Visit", which includes specific vision screening, blood pressure measurement, and OCT imaging as per study protocol. Patients will be given a bottle containing 28 tablets of eplerenone 50mg, and will start eplerenone the same day. Medication will be provided by the Tufts Research

Pharmacy. Patients will then return to the clinic at 1 week, 2 weeks, and 4 weeks after baseline.

2. At baseline and all subsequent study visits, participants will be examined by an ophthalmologist at the NEEC using conventional techniques. The eye examination will include visual acuity testing using the ETDRS chart, extra-ocular motility, intraocular pressure measurement, and a routine slit lamp and dilated fundus examination. Manifest refraction will be performed at the baseline visit and at week 4. Pupils will be dilated with standard dilating drops given via one drop to both eyes one-half hour prior to eye examination).
3. *Visual Acuity*: Best-corrected visual acuity is a secondary endpoint in this study. Refraction and testing of visual acuity will be standardized using the ETDRS protocol. Certified refractionists and visual acuity examiners will be used. Examination lanes will utilize a starting distance of 4 meters according to the ETDRS protocol. Refraction will be performed at the baseline visit and at 4 weeks.
4. *Optical Coherence Tomography (OCT)*: OCT images will be acquired at each visit. The ophthalmic photographers will be responsible for explaining how the non-invasive OCT images are obtained, as occurs with all of our patients routinely. OCT will be obtained using a commercially available, FDA-approved system, the Cirrus HD-OCT (Carl Zeiss Meditec, Dublin, CA). Both eyes will be scanned using an internal fixation point. The length of the test using Cirrus HD-OCT is approximately 5 minutes per eye. Scan protocols capturing 1 to 5 images with high image definition from a focal location can be used for qualitative assessment of the retinal structure. A denser scan pattern, the macular cube scan, captures 128 512-line images within a 6 mm x 6 mm area centered on the macula, allowing calculation of retinal thicknesses and volumes with high precision. Scan protocols include:
 - a. Cirrus HD-OCT 5 line raster scan
 - b. Cirrus HD-OCT single line scan
 - c. Cirrus HD-OCT 512x128 macular cube scan
 - d. Cirrus HD-OCT Enhanced Depth Imaging (EDI) scan
5. *Fluorescein Angiography*: Fluorescein angiography will be acquired at diagnosis and at 4 weeks after treatment initiation. Angiography will be explained to patients by either the physician or the ophthalmic nurse administering the intravenous dye. Patients routinely give verbal consent stating they understand the procedure and potential risks of fluorescein angiography. The procedure involved a special water-soluble dye (fluorescein) that is injected intravenously. As the dye passes through the blood vessels of the choroid and retina, the photographer takes a series of photographs in rapid succession, over a period of 5-10 minutes. The possible side effects of fluorescein angiography are discussed below.

Laboratory Testing: After initial screening, serum potassium and creatinine will be evaluated at 1 and 4 weeks after baseline. *See below for dosing adjustment instructions based on potassium levels.* Additional serum tests of electrolytes, liver function tests, uric acid, and a fasting cholesterol panel will be obtained before treatment and 4 weeks after baseline

Baseline and 4-week visits: Serum potassium, sodium, BUN, creatinine, glucose, chloride, total CO₂, calcium, AST, ALT, GGT, alkaline phosphatase, total and direct bilirubin, uric acid, albumin, total protein, fasting total cholesterol, fasting LDL, fasting LDL, fasting triglycerides. The initial and final blood draws will be roughly 7.5 to 10 ml of blood, or 2 teaspoons.

6. **1-week visit:** Serum potassium and serum creatinine. The 1-week blood draws will be roughly 4 ml of blood, or 1 teaspoon.

7. **Blood pressure:** Systolic and diastolic blood pressure will be recorded at all visits. Blood pressure will be measured in the seated position. When blood pressure is scheduled at the same time point as a blood sample draw, the blood pressure will be measured first.

8. The subject's participation in the research may be terminated by the principal investigator or co-investigator if there is any type of medical emergency or urgency that needs to be attended to first. If a subject decides to withdraw from the research, the patient will be offered routine ophthalmologic care at NEEC. If the patient prefers, he or she can be referred to an outside ophthalmologist for continued eye care. The subject's data and collected blood and urine samples will be discarded, although the reason for screen failure will be noted after the patient demographic data is de-identified.

Eligibility

Both male and female participants of any race will be enrolled.

Inclusion Criteria:

1. Age 18 or over
2. Ability to give written informed consent
3. Presence of sub-retinal fluid under the fovea as seen on OCT
4. Diagnosis of Acute or Chronic CSCR:
 - a. Acute CSCR: First presentation to eye clinic with visual symptoms, including decreased vision or visual distortion, and the characteristic appearance of CSCR on examination, fluorescein angiography, and OCT.
 - b. Chronic CSCR: Previous diagnosis of CSCR, persistent subretinal fluid on OCT \geq 3 months after initial presentation to the eye clinic, and <50%

reduction in fluid thickness on OCT after 3 months. *Patients who have had previous treatment for CSCR may be included.*

Exclusion Criteria:

1. Age less than 18
2. Persons with impaired decision-making ability.
3. Women who are known to be pregnant or are actively trying to conceive.
4. Additional eye disease affecting the macula or posterior retina.
5. At screening, serum potassium concentration ≥ 5.0 mEq/L, a serum creatinine concentration >2 mg/dL in men and >1.8 mg/dL in women, or a creatinine clearance <50 mL/min, and during concomitant administration of potassium supplements, potassium-sparing diuretics, and/or potent CYP3A4 inhibitors (amifostine, cyclosporine, fluconazole, itraconazole, ketoconazole, mifepristone, posaconazole, potassium salts, Rituximab, tacrolimus, voriconazole, nefazodone, troleandomycin, clarithromycin, ritonavir, or nelfinavir).
6. Patients with type 2 diabetes will be screened for microalbuminuria with a urinalysis. If microalbuminuria is present, these patients will be excluded.

Data Elements

The data elements to be collected from each participant include age, gender, visual acuity, intraocular pressure, lens status, and retinal examination findings, color fundus photographs, fluorescein angiography images, and OCT images.

Primary Outcome

Presence or absence of subretinal fluid and/or intraretinal fluid on OCT after 4 weeks of treatment with 50 mg of eplerenone.

Secondary (Exploratory) Outcomes

- Change in central macular circle thickness on OCT, automatically calculated with OCT software after 1, 2, and 4 weeks of treatment
- Change in thickness of subretinal fluid under the fovea on OCT, manually calculated after 1, 2, and 4 weeks of treatment
- Change in thickness of choroid under the fovea on enhanced-depth imaging OCT, manually calculated, after 1, 2, and 4 weeks of treatment
- Change in best-corrected visual acuity before and after 4 weeks of treatment
- Change in dye leakage characteristics on fluorescein angiography before and after 4 weeks of treatment
- Change in the same OCT characteristics listed above, in the fellow eye
- Proportion of acute vs. chronic CSCR patients
- Safety and tolerability characteristics in this patient population via clinical laboratory data, blood pressure, and adverse events

Data Safety and Monitoring Plan

See below for details regarding monitoring of adverse events (AEs) and serious adverse events (SAEs). Data will be monitored with the patients' safety in mind. All adverse effects will be recorded by the Principal Investigator and Co-Investigators and will be reported to the IRB at the conclusion of the study. Should an SAE occur, it will be reported immediately to the Tufts MC / TUHS IRB by the Principal Investigator within 24 hours. The Principal Investigator and Co-Investigators will be responsible for collecting the patient data information. The information will then be de-identified and coded. The key to the code will only be accessed by the investigators.

Dose adjustment and/or stopping criteria

Serum potassium criteria

If serum potassium is ≥ 5.0 mEq/L and < 5.5 mEq/L at 1 week after initiation, dosing will be decreased to 25 mg every day and serum potassium will be rechecked at 1 week. If serum potassium is still ≥ 5.0 mEq/L and < 5.5 mEq/L after 1 additional week, dosing will be decreased to 25 mg every other day and serum potassium will be rechecked at 1 week. If serum potassium is still ≥ 5.0 mEq/L and < 5.5 mEq/L after 1 additional week, dosing will be withheld. If serum potassium is ≥ 5.5 mEq/L at 1 week, eplerenone will be withheld.

See below for definition of adverse events and serious adverse events.

Statistical Analysis

The primary outcome will be described by the proportion of patients without subretinal fluid on OCT at the end of the study period (see below for sample size and precision estimates). The 95% confidence interval (CI) for this proportion will also be estimated. Descriptive statistics are considered appropriate for this pilot study since there is currently no standard treatment for CSCR, and the data from this study may be used to design future, rigorous trials of eplerenone.

Changes in continuous secondary outcome measures will be described using mean, median, min/max, and standard deviations, and categorical secondary outcome measures will be described using frequencies and proportions.

Sample Size and Precision Calculations

The natural history of acute CSCR is to improve on its own. Studies have shown, however, that fluid resolution typically takes at least 6 weeks, and often takes as long as 3 months or longer. In a randomized study by Chan et al examining effects of half-dose photodynamic therapy in patients with acute CSCR, 20% of patients had complete resolution of fluid on OCT after 4 weeks, compared to 80% of patients treated with PDT.[12] Similar rates of complete fluid resolution have been reported after treatment with PDT, as well as in a small sample of patients with chronic CSCR treated with eplerenone.[1, 22-26] Based on these assumptions, a calculation was performed to determine the width of confidence intervals for the proportion of patients successfully

treated with eplerenone. If the treatment is effective for 70% of patients, a sample size of 10 patients will give a 95% confidence interval width of 0.586 that includes a lower bound of 0.348 (see range of widths with sample sizes of 10 and 15 below). The Research Design Center of the Clinical and Translational Sciences Institute at Tufts Medical Center assisted with these calculations.

Numeric Results for Two-Sided Confidence Intervals for One Proportion Confidence Interval Formula: Exact

Confidence Level	Sample Size (N)	Target Width	Actual Width	Proportion (P)	Lower Limit	Upper Limit	Width if P = 0.5
0.950	10		0.586	0.700	0.348	0.933	0.626
0.950	10		0.531	0.800	0.444	0.975	0.626
0.950	10		0.442	0.900	0.555	0.997	0.626
0.950	15		0.487	0.700	0.416	0.903	0.522
0.950	15		0.438	0.800	0.519	0.957	0.522
0.950	15		0.356	0.900	0.637	0.993	0.522

References

Flleiss, J. L., Levin, B., Paik, M.C. 2003. Statistical Methods for Rates and Proportions. Third Edition. John Wiley & Sons. New York.
 Newcombe, R. G. 1998. 'Two-Sided Confidence Intervals for the Single Proportion: Comparison of Seven Methods.' *Statistics in Medicine*, 17, pp. 857-872.

Safety Analysis

Safety data will be presented in tabular format and will be summarized descriptively.

PART III

1. How will participants be recruited?
 Participants will be recruited from the practices of the primary investigator and co-investigators.
2. Number of participants needed?
 The maximum number of participants over the entire study is expected to be 20.
3. Will participants receive any payment or other compensation for participation?
 No. There are no costs to subjects participating in this research study and he or she will not be billed for the visit. Eplerenone will be provided by the New England Eye Center.
4. Will participants be studied outside NEEC premises?
 No.

5. Will the facilities of the Clinical Research Center be used?
No.
6. Will drugs be used?
Yes. Eplerenone 50mg, an oral medication FDA-approved for use in systemic hypertension and congestive heart failure, will be used off-label for treatment of all patients in this study. Patients will be provided the medication by the investigational team. Funding is being provided by the Research Fund of the Ophthalmology Department at Tufts Medical Center.
7. Will radiation or radioactive materials be employed?
No.
8. Will special diets be used?
No.
9. Will participants experience physical pain or stress?
While some patients experience distorted vision as a result of CSCR, no additional physical distress to patients is expected as a result of this study.
10. Will a questionnaire be used?
No.
11. Are personal interviews involved?
No.
12. Will participants experience psychological stress?
No.
13. Does this study involve planned deception of participants?
No.
14. Can information acquired through this investigation adversely affect a participant's relationships with other individuals?
No.
15. Please explain how subjects' anonymity will be protected, and/or confidentiality of data will be preserved.
The data obtained from the study will be retained by [name] and will be stored at NEEC for a minimum of 8 years per institutional policy. Members of the research study team including the principle and co-investigators will analyze the data. If results of this study are reported in medical journals or at meetings, subjects will not be identified by name, by

recognizable photograph, or by any other means. The subjects' medical records will be maintained according to the NEEC requirements.

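### Inclusion 3 does not require subfoveal fluid in the study eye on the Treatment Initiation Visit OCT, so an eye that cleared before the first dose can count as a treatment success

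*Combined protocol and SAP*

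**What the plan says.** Part II, Eligibility, Inclusion Criteria, item 3 reads in full "Presence of sub-retinal fluid under the fovea as seen on OCT". Exclusion item 5, in the same section, ties its laboratory limits to screening; the fluid criterion has no such anchor.

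The sequence before the first tablet is:

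- **Diagnosis.** Imaging includes OCT, but Initial Diagnosis and Enrollment, item 1 says of the diagnostic work-up: "These tests are done routinely in the eye clinic and are not included as part of the study protocol".
- **Decision.** Item 2 of that section says of patients that "they can consider whether or not to enroll in the study, and enroll at a later date if they so choose". It sets no limit.
- **Screening.** Item 4: "Prior to starting eplerenone therapy, there will be a screening period (≤ 1 week) when serum potassium and creatinine will be evaluated". The other tests described there are blood and urine tests; no OCT is listed.
- **Treatment Initiation Visit.** Study Visits, item 1 describes this as the first official study visit, "which includes specific vision screening, blood pressure measurement, and OCT imaging as per study protocol". Eplerenone starts the same day. Nothing says what happens if that scan shows no fluid.

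The Primary Outcome is fluid status (subretinal and/or intraretinal) after 4 weeks. Statistical Analysis reports the proportion of patients without subretinal fluid at the end of the study, with a 95% CI. Neither is conditional on fluid at the first dose.

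On the eye, Study Design says "Only one eye of a participant will be included in the study, although both eyes will be evaluated" and "In patients with bilateral CSCR, the worse eye will be the study eye". It names no measure of worse and makes no link to inclusion 3.

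**The concern.** Acute CSCR clears without treatment, as the plan itself says. A patient can meet inclusion 3 on the diagnostic scan, take some weeks to decide, complete screening and start the drug with an eye that is already dry. If the eye is still dry at week 4 it enters the numerator, although eplerenone had nothing to resolve.

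The error has one direction. It can only raise the primary proportion, and a single-arm study has no comparison group in which the same error would cancel. The same eye has a foveal fluid thickness of zero at baseline and cannot improve on the secondary fluid-thickness outcome, so it dilutes that result while inflating the primary one.

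In bilateral disease there is a second, weaker gap. If worse is judged by acuity, say, the chosen study eye need not be the eye with subfoveal fluid.

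**Working it through.** **Plan's own figure.** Exact (Clopper-Pearson) 95% limits for 7/10 are 0.348 to 0.933, width 0.586. This matches Sample Size and Precision Calculations. The other five rows of that table, and both widths at P = 0.5, also reproduce. The precision figures are not in dispute.

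**Inputs from the documents.** Planned enrolment is 20 (Study Design). Spontaneous clearing of acute disease by 1 month is given under Prognosis of CSCR as about 20% (4/19 = 21.1%; 6/29 = 20.7%), and as 10% or less in the clinic's own experience. Another series of 20 acute patients had a mean time to clearing of 65 days, range 28 to 155. The planning success rate is 70%.

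**Assumptions.** The documents do not give the acute/chronic mix or the delay before dosing. I assume a constant clearing hazard within the month, that chronic eyes do not clear while waiting, and that eyes dry at the first dose stay dry to week 4.

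**Step 1: chance of being dry at the first dose.** With 28-day clearing rate r and a gap of d days, q = 1 − (1 − r)^(d/28).

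| Gap | r | q | Expected dry eyes |
|---|---|---|---|
| 7 days, all 20 acute | 10% | 0.026 | 0.52 |
| 7 days, all 20 acute | 20% | 0.054 | 1.09 |
| 28 days, 10 of 20 acute | 10% | 0.10 | 1.0 |
| 28 days, 10 of 20 acute | 20% | 0.20 | 2.0 |

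The 7-day rows are upper figures. They take every patient as acute, and the series with no clearing before day 28 puts q near 0. The range for a 1-week gap is therefore about 0 to 1 eye. In the 28-day rows, 1 eye sits at the top of the clinic's own range, since its figure is 10% or less.

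**Step 2: effect on the primary proportion.** If a fraction f of study eyes is dry at the first dose and the true rate in eyes with fluid is p, the observed rate is f + (1 − f)p. The net shift is f(1 − p).

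- 1 of 20 dry (f = 0.05): at p = 0.70 the shift is 0.05 × 0.30 = 1.5 points (observed 71.5%); at p = 0.20 it is 0.05 × 0.80 = 4 points (24%).
- 2 of 20 dry (f = 0.10): at p = 0.70 it is 0.10 × 0.30 = 3 points (73%); at p = 0.20 it is 0.10 × 0.80 = 8 points (28%).

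The distortion is largest when the drug does little.

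**Step 3: the same from observed counts.** 14/20 = 70.0% (exact 95% CI 0.457 to 0.881). With one already-dry success removed it is 13/19 = 68.4% (0.434 to 0.874). With two removed it is 12/18 = 66.7% (0.410 to 0.867).

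**The case against.** The natural reading of inclusion 3 is a present state, judged at enrolment, and the open-ended wait falls before enrolment. After that the plan allows at most 1 week of screening and 4 to 5 weeks in total. The plan also says that fluid typically takes at least 6 weeks to clear, and it defines acute disease by first presentation. This is a descriptive pilot with no test or decision threshold, and a shift of 1.5 to 3 points is small against a CI some 42 points wide. OCT is taken at every visit, so a dry baseline would show in the data.

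Much of this stands as to size. It does not close the gap. Later enrolment is expressly allowed, no study OCT is listed before the Treatment Initiation Visit, and no rule stops an old diagnostic scan from serving as evidence of fluid. Seeing a dry baseline in the data helps only if the plan says beforehand how to handle it; otherwise dropping the eye is a post hoc exclusion.

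A reader might infer more than the documents support:

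- **That 1 to 2 dry eyes inflate the result by 5 to 10 points.** That is their gross share of 20. It equals the net shift only if none of them would have cleared during the study.
- **That a study eye without subfoveal fluid is bound to succeed.** The primary outcome counts any subretinal or intraretinal fluid, and such an eye may have fluid elsewhere. Even a fully dry eye can relapse: the plan cites recurrence in 30 to 50% of patients.
- **That nothing else in the study bears on efficacy.** The secondary outcomes include macular, fluid and choroidal thickness, acuity and angiographic leakage.

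**Conclusion.** The concern holds at moderate severity. Followed as written, the plan can admit an eye that resolved before treatment and count it in the numerator of an uncontrolled estimate, always in the drug's favour. With prompt enrolment the effect is about 0 to 1 of 20 eyes. It reaches 1 to 2 eyes if 10 of 20 patients are acute and wait about 4 weeks, which is a net 1.5 to 3 points at a true rate of 70% or 4 to 8 points at 20%. The mix, the delay and the constant hazard are assumptions.

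The study-eye gap is secondary. In unilateral disease the affected eye is implied, so it matters only in bilateral cases. Neither gap makes the study uninterpretable, and the documents do not support calling this a defect that must be repaired before the study can proceed.

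**What to change.** Reword inclusion 3 along these lines: *Subretinal fluid under the fovea of the study eye on the Treatment Initiation Visit OCT, confirmed before enrolment is completed.* Add that an eye without fluid on that scan is recorded as resolved before treatment, treated as a screen failure, and kept out of the primary proportion.

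As a secondary clarification, state under Study Design that the study eye must itself meet inclusion 3, and name in advance the measure that decides which eye is worse when both qualify. Greater subfoveal fluid thickness is one option. It suits the outcome, but it is not the only defensible choice.

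The cost is a few sentences and an occasional late screen failure. The OCT is already scheduled at that visit, so no procedure is added.
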